8.3.6 SERIOUS ADVERSE EVENT REPORTING

All patients are monitored for respiratory depression. All cases of this are reported to our internal PI committee and reviewed independently.

8.3.7 REPORTING EVENTS TO PARTICIPANTS

All AEs are reported to participants.

8.3.8 EVENTS OF SPECIAL INTEREST

N/A

8.3.9 REPORTING OF PREGNANCY

N/A

8.4 UNANTICIPATED PROBLEMS

8.4.1 DEFINITION OF UNANTICIPATED PROBLEMS (UP)

There are no unanticipated problems with this study, however, should any issue occur the PI will be available to discuss

8.4.2 UNANTICIPATED PROBLEM REPORTING

At any time any participant, clinical team member, or study team member can report an event to the PI.

8.4.3 REPORTING UNANTICIPATED PROBLEMS TO PARTICIPANTS

Those that may impact patient care and well being will be reported to all participants.

9 STATISTICAL CONSIDERATIONS

9.1 STATISTICAL HYPOTHESES

- Primary Efficacy Endpoint(s):

Opiate consumption at 24 hours (Wilcoxon Rank Sum)

- Secondary Efficacy Endpoint(s):

Recovery score at 24 Hours (Wilcoxon Rank Sum)

Breast feeding at 1 week (Chi Square)

Depression screen at 6 weeks (Wilcoxon Rank Sum)

9.2 SAMPLE SIZE DETERMINATION

Based on other works it was determined that for a 25% reduction in opiate utilization we needed 60 patients for each group. To account for drop off we will recruit 150 patients per group for a total of 300 patients

9.3 POPULATIONS FOR ANALYSES

This will be intention to treat for all randomized participants.

9.4 STATISTICAL ANALYSES

9.4.1 GENERAL APPROACH

Wilcoxon rank sum for continuous variables, chi square for categorical

9.4.2 ANALYSIS OF THE PRIMARY EFFICACY ENDPOINT(S)

Wilcoxon rank sum

9.4.3 ANALYSIS OF THE SECONDARY ENDPOINT(S)

Recovery score and depression score: Wilcoxon Rank Sum, Breast feeding: Chi square

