1 PROTOCOL SUMMARY

1.1 SYNOPSIS

Title:	Duramorph Study Design: Prospective, Randomized Double Blinded
Study Description:	Prospective double blind randomized control trial
Objectives:	Primary Objective: Analyze impact of epidural morphine on pain management for vaginal delivery VD Secondary Objectives: Analyze impact of epidural morphine on recovery and depression
Endpoints:	Primary Endpoint: Opiate consumption at 24 hours Secondary Endpoints: Pain score at 24 hours, obstetric recovery score at 24 hours, Edinburgh post partum depression scale at 6 weeks, breast feeding success at 1 week
Study Population:	Pregnant women over 18
Phase:	4
Description of Sites/Facilities Enrolling Participants:	KP2 Labor floor at Mount Sinai Hospital
Description of Study Intervention:	Epidural morphine 2mg vs placebo
Study Duration:	4 years
Participant Duration:	6 weeks

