2 INTRODUCTION

2.1 STUDY RATIONALE

There is no current standard of care for post vaginal delivery pain. Many different options exist, however, their impact on minimizing opiate utilization have been minimal. As such, we are investigating the utility of a single dose of preservative free morphine on pain scores in the post partum period.

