2.2 BACKGROUND

There is no gold standard for pain management in NSVD. There is some evidence that preservative free morphine is effective at pain relief for cesarean deliveries. The relationship between pain and epidural morphine for NSVD has not been investigated.

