3 OBJECTIVES AND ENDPOINTS

OBJECTIVES	ENDPOINTS	JUSTIFICATION FOR ENDPOINTS
Primary		
	Opiate consumption at 24 hours	Opiate use should be minimized due to side effects
Secondary		
	Pain score at 24 hours Recovery score at 24 hours Breast feeding rate at 1 week Post partum depression screen at 6 weeks	Better pain control is good endpoint, as is recovery. Breastfeeding can have long term impacts on both mom and baby and it's impact should be investigated. Depression is a major issue post partum and controlling pain in the immediate post partum period may help with that.
Tertiary/Exploratory		

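### Does leaving the 24-hour pain score out of the lists in 9.1 and 9.4.3 leave that endpoint without a planned analysis?

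*Combined protocol and SAP*

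**What the plan says.** The synopsis (1.1) opens its list of secondary endpoints with pain: "Secondary Endpoints: Pain score at 24 hours, obstetric recovery score at 24 hours". It then adds the depression scale and breast feeding. The table in section 3 names the same four: "Pain score at 24 hours Recovery score at 24 hours Breast feeding rate at 1 week Post partum depression screen at 6 weeks". Section 8.1 says that a Likert pain score is obtained at 24 hours, together with the recovery score and opiate consumption.

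The statistical section is shorter by one. Under secondary endpoints, 9.1 begins with the recovery score ("Recovery score at 24 Hours (Wilcoxon Rank Sum", in its bracketed style), continues with breast feeding and the depression screen, and stops. Section 9.4.3 covers the same three: "Recovery score and depression score: Wilcoxon Rank Sum, Breast feeding: Chi square". Before that, 9.4.1 sets a rule by type of variable: "Wilcoxon rank sum for continuous variables, chi square for categorical".

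Pain is prominent in the introductory text. Section 2.1 says "we are investigating the utility of a single dose of preservative free morphine on pain scores in the post partum period", section 2.2 says "The relationship between pain and epidural morphine for NSVD has not been investigated", and the synopsis gives "Primary Objective: Analyze impact of epidural morphine on pain management for vaginal delivery VD".

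**The concern.** The endpoint missing from the analysis lists is the one closest to the stated rationale. Someone who worked from 9.1 and 9.4.3 alone would report no comparison of pain scores. If a pain result did appear, a sceptical reader could ask whether its test had been chosen after the data were seen. If none appeared, the reader could ask whether it had been dropped.

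The choice of test adds to the worry. A Likert score is ordinal, and 9.4.1 divides variables only into continuous and categorical. In principle, one analyst could use the rank-sum test and another chi-square on the same data. The primary endpoint, opiate consumption, reflects pain only indirectly, so a reader would want the pain score beside it to interpret a fall in opiate use.

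**Working it through.** The plan states no figure on this point, so the check is to set the sections side by side.

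| Secondary endpoint | 1.1 | 3 | Collected in | 9.1 | 9.4.3 |
|---|---|---|---|---|---|
| Pain score, 24 hours | yes | yes | 8.1 | absent | absent |
| Recovery score, 24 hours | yes | yes | 8.1 | Wilcoxon | Wilcoxon |
| Breast feeding, 1 week | yes | yes | 8.2 | chi-square | chi-square |
| Depression screen, 6 weeks | yes | yes | 8.2 | Wilcoxon | Wilcoxon |

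Four endpoints are defined and three are listed for analysis: 4 − 3 = 1 missing, the same one in both places. The mismatch is real.

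The next question is what an analyst would lack because of it.

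1. *Variable and time point.* Both are given in 1.1 and section 3, and repeated in 8.1.
2. *Population.* Section 9.3 applies intention to treat to all randomized participants and makes no exception by endpoint.
3. *Test.* Section 9.4.1 covers every variable by type. The only doubt is which type a Likert score belongs to. The plan's own practice answers that: both other scores, recovery and depression, go to the rank-sum test, and chi-square is kept for breast feeding, which section 3 expresses as a rate. A third score belongs with the first two. The rank-sum test handles ties and needs no stated number of levels, so the undefined Likert scale does not block the analysis. The documents give no range for the recovery score either, and it still has an assigned test.
4. *Hypothesis.* Despite its title, 9.1 states no null or alternative hypothesis for any endpoint. Each entry is a name with a test in brackets. The pain score therefore lacks a list entry, not a hypothesis that the others have.

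The last question is whether any figure depends on the number of listed endpoints. The sample size in 9.2 (60 per group needed, 150 per group recruited, 2 × 150 = 300 in total) rests on a 25% reduction in opiate use and does not involve the pain score. Section 9 divides no significance level among the secondary endpoints, so counting four instead of three alters no threshold for the others. The power of a rank-sum comparison of pain scores is the same whether or not a line for it appears in 9.4.3, so a power calculation would not measure this omission.

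**The case for a change.** The strongest case for a change is this. The general rule was evidently not meant to stand alone, because the authors restated it endpoint by endpoint for the other three. The same endpoint is missing twice, and neither list reads as a set of examples. Section 2.1 puts pain scores at the centre. A Likert score sits awkwardly between the two types in 9.4.1. One added line in each list, before unblinding, would remove any doubt that the pain comparison was planned.

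Some of this stands. The lists do disagree, there is no sign of a redaction at either place, and the remedy would cost almost nothing. The consequences are weaker than they appear:

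- The record that the comparison was planned already exists in 1.1 and section 3. An omitted pain result could be recognised against those lists, and a reported one could not fairly be called unplanned.
- Missing the comparison altogether would require passing over the general approach that opens section 9.4 as well as two endpoint lists.
- Section 2.1 gives no 24-hour time point, and the sentence before the one quoted is about reducing opiate use. That aim is carried by the primary endpoint, which has its test in both 9.1 and 9.4.2. The primary objective of pain management is therefore not left without an analysis.
- The pain score cannot be called the only direct measure of pain in the plan, because the items of the recovery score are not described.
- The missing levels and anchors of the Likert scale concern how the instrument is defined. They are separate from the gap in the analysis lists.

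**Conclusion.** The concern does not call for a change. One of four secondary endpoints was left off two lists by a clerical slip, and the rest of the plan fills the gap: the pain score at 24 hours is to be compared between arms by the Wilcoxon rank-sum test in all randomized participants. Writing that line in would record what analysts would do anyway. No result, sample size, threshold or conclusion would differ.

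This rests on two assumptions: that analysts read 9.4.1 together with the endpoint lists in 1.1 and 3, and that they treat the pain score as the plan treats its recovery and depression scores. Nothing in the documents points the other way.

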1.2 SCHEMA

1. Obtain consent
2. 1 hour delivery administer study drug or placebo
3. 24 hours after collect data on opiate administration, pain score, and recovery score
4. 1 week after administration call patient inquire about breast feeding
5. At 6 weeks after administration call patient and administer post partum depression screen

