5 STUDY POPULATION

5.1 INCLUSION CRITERIA

18 years old, pregnant, presenting for VD

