5.2 EXCLUSION CRITERIA

Refusal of neuraxial anesthesia, allergy to morphine, patients with chronic pain syndromes or chronic opiate use.

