8.2 SAFETY AND OTHER ASSESSMENTS

At one week we will ask patients about breast feeding. At 6 weeks we will ask about depression

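### No feeding intention is recorded before randomization and breast feeding success is undefined, so women not planning to breast feed probably dilute the 1-week comparison

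*Combined protocol and SAP*

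**What the plan says.** The endpoint has two names. Section 1.1 lists "breast feeding success at 1 week" and the table in Section 3 lists "Breast feeding rate at 1 week". Neither is defined, and no denominator is given.

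Eligibility (Section 5.1) is "18 years old, pregnant, presenting for VD". The exclusions in Section 5.2 are "Refusal of neuraxial anesthesia, allergy to morphine, patients with chronic pain syndromes or chronic opiate use". Neither section refers to feeding plans.

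Feeding first appears after dosing. The schema in Section 1.2 has "1 week after administration call patient inquire about breast feeding", Section 1.3 repeats that step, and Section 8.2 says "At one week we will ask patients about breast feeding". No earlier step asks about feeding.

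On analysis, Section 9.3 says "This will be intention to treat for all randomized participants", and Section 9.4.3 says "Breast feeding: Chi square". Section 9.4.5 names no baseline variables and Section 9.4.7 marks subgroup analyses as not applicable. Feeding intention is not mentioned anywhere in the document.

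**The concern.** Section 2.3.3 suggests that the study dose may lead to more breast feeding, and Section 3 justifies the endpoint by long-term effects on mother and baby. That hypothesis mainly concerns women who want to breast feed. A woman who decided before labor not to do so is unlikely to change course because of the dose. If she nevertheless sits in the denominator as not breast feeding, she adds no information about the effect and pulls the two arms together.

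Two things are at stake. First, a null result in all women would say little about whether pain control helps those who want to breast feed. Second, without a baseline record nobody can see or adjust for a chance difference between arms in the share of non-intenders.

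The omission cannot be repaired later for women already treated, because intention asked after dosing could be affected by treatment and by how feeding went.

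**Working it through.** **Plan's own figure.** There is none for this endpoint. The figures in Section 9.2 (60 per group needed, 150 per group recruited) concern opiate use, so no stated power for breast feeding can be reproduced.

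**Inputs.**
- From Section 9.2: n = 150 per arm, equal allocation. Treating all 150 as analysed is the favourable case, because Section 9.2 recruits 150 to allow for drop-off.
- Assumed, since the documents give no rates: success among intenders p1 (placebo) and p2 (morphine); share of non-intenders q; no success among non-intenders in either arm; two-sided 5% level.

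**Step 1: dilution.** In all randomized women the rates become p1(1−q) and p2(1−q). The risk difference is (p2−p1)(1−q), and the risk ratio p2/p1 is unchanged. With 75% against 87% and q = 0.20:
- all women: 0.75 × 0.80 = 60.0% and 0.87 × 0.80 = 69.6%, a difference of 9.6 points;
- intenders: 12 points, in 150 × 0.80 = 120 per arm.

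**Step 2: power.** For a two-proportion comparison, power = Φ[(d − 1.96·SE0)/SE1]. Here d is the difference in rates, p̄ is the mean of the two rates, SE0 = √(2p̄(1−p̄)/n), and SE1 is the square root of the sum of the two arms' binomial variances, each divided by n.
- All women, n = 150: p̄ = 0.648, SE0 = 0.0551, SE1 = 0.0549. (0.096 − 1.96 × 0.0551)/0.0549 = −0.22, so power is 41%.
- Intenders, n = 120: p̄ = 0.81, SE0 = 0.0506, SE1 = 0.0500. (0.12 − 1.96 × 0.0506)/0.0500 = 0.42, so power is 66%.

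**Step 3: range.** Power at 150 randomized and analysed per arm, all women against intenders only:

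| Success among intenders | 95% intend | 90% intend | 80% intend | 70% intend |
|---|---|---|---|---|
| 75% v 87% | 65 v 74% | 56 v 71% | 41 v 66% | 31 v 60% |
| 75% v 85% | 49 v 56% | 41 v 54% | 30 v 49% | 23 v 44% |
| 70% v 85% | 80 v 86% | 72 v 84% | 57 v 80% | 45 v 74% |

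The gain fades at the edges. At 75% against 87% with 98% intending, power is 71% against 75%. At 75% against 80% with 80% intending, it is 11% against 15%.

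**Step 4: chance imbalance.** The SD of the between-arm difference in non-intender share is √(2q(1−q)/150). This is 3.5 points at q = 0.10, 4.6 at q = 0.20 and 5.3 at q = 0.30. In the 75% against 85% case, the all-women difference to be detected is only 9, 8 and 7 points at those shares.

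**The case against.** The strongest reply is that the planned comparison is sound. Intention is balanced in expectation by randomization, so the all-randomized test is unbiased. If non-intenders never succeed, the risk ratio is also unchanged. It answers a legitimate question: what happens to the feeding rate if the dose is given to everyone eligible? Restricting to intenders changes the estimand and narrows the population. All of this stands, and it is why the all-randomized comparison should be kept.

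A reader might infer that the plan scores non-intenders as failures. The documents do not say so. With success and rate both undefined, that is only the natural reading of Sections 9.3 and 9.4.3, and success could instead mean success among women who tried. But under that second reading the plan specifies nothing before randomization to identify those women.

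A reader might also infer that the dose can have no effect on a non-intender. That too is an assumption. Some women may change their minds after delivery, and an intender-only analysis would miss any effect in them.

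Finally, the datasheets mentioned in Section 6.4 are not itemised and might hold a feeding question. So the supportable statement is that the plan specifies none, not that none exists. Even if one does exist, no planned analysis uses it.

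**Conclusion.** The point holds as a gap in definition and baseline data, with a likely loss of power. It is not an error or a bias in the planned test. No pre-randomization feeding intention is specified, the endpoint and its denominator are undefined, and on the natural reading non-intenders dilute the risk difference by about the factor (1−q).

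In the main illustration the intender analysis gains about 9 points of power when 95% intend and about 29 points when 70% intend. It had more power in every case run, though by only a few points when nearly all women intend or the effect is small. These sizes rest on assumed feeding rates, assumed intention shares, no success among non-intenders and full follow-up.

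The intender analysis would not make the endpoint well powered in the main illustration (60 to 74%), so a null there could still be inconclusive. Section 7.3 says that the study is powered for 24-hour opiate consumption, and that conclusion is untouched. Nor does the dilution produce a false claim of benefit, since it acts toward the null.

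**What to change.** 1. Add one yes/no question on intention to breast feed at consent, before randomization. Sections 5.4 and 10.1.1 already place consent in labor once the epidural is working, so no new contact is needed. List the answer among the baseline variables in Section 9.4.5.
2. Use one name for the endpoint in Sections 1.1 and 3, and define what counts as breast feeding at 1 week and who is in the denominator.
3. In Section 9.4.3, keep the all-randomized chi-square comparison and prespecify beside it an analysis among women who intended to breast feed, analysed as randomized, or a comparison stratified by intention. Because intention is fixed before allocation, either remains a valid randomized comparison. State which analysis is the main one for this endpoint.
4. If some women have already been dosed without being asked, do not fill the gap with an answer obtained at the 1-week call.

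The cost is one question and a few lines of text. The intender analysis has a smaller denominator, and its result applies to women who intend to breast feed.

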9.4.4 SAFETY ANALYSES

N/A

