2.3 RISK/BENEFIT ASSESSMENT

2.3.1 KNOWN POTENTIAL RISKS

Risks can include nausea, vomiting, itching, respiratory depression

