2.3.3 ASSESSMENT OF POTENTIAL RISKS AND BENEFITS

Benefits include less oral and IV opiate use which also cause nausea, itching and respiratory depression. Benefits may also include a faster recovery and more breast feeding. The risks of this dose of morphine are small and have been used for cesarean delivery for decades.

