6.5 CONCOMITANT THERAPY

6.5.1 RESCUE MEDICINE

Any patients on opiates or with an allergy to morphine are excluded and as such there is no risk for synergistic effects of the study drug. As per our CD protocol, we provide the same rescue doses of medications for morphine including ondanstetron, diphenhydramine, and nalxone all as needed.

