8 STUDY ASSESSMENTS AND PROCEDURES

8.1 EFFICACY ASSESSMENTS

At 24 hours we will get a likert pain score, as well as a recovery score. We will also obtain opiate consumption for this time.

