8.3.3.3 EXPECTEDNESS

We expect to have cases of nausea and itching, we anticipate no cases of respiratory depression

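### No by-arm summary of adverse events is planned and no scheduled contact asks about nausea, vomiting or itching, so lower opiate consumption cannot show fewer side effects

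*Combined protocol and SAP*

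**What the plan says.** **Analysis.** The section headed "9.4.4 SAFETY ANALYSES" contains only N/A. Sections 9.1, 9.4.2 and 9.4.3 name opiate consumption, recovery score, depression score and breast feeding. Section 9.4.1 assigns a test to each type of variable but mentions no adverse event.

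**Data collection.** Section 8.1 says "At 24 hours we will get a likert pain score, as well as a recovery score" and adds opiate consumption. Section 8.2, although titled as covering safety, says only "At one week we will ask patients about breast feeding. At 6 weeks we will ask about depression". The schema (1.2) and the schedule of activities (1.3) list the same content. Under 8.3.5, adverse events reach the study team when a woman reports them at a follow-up or when clinical staff raise them. Respiratory depression is handled differently: 8.3.6 has every woman monitored for it, and 8.3.6 and 10.1.8 have cases reviewed.

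**Rationale.** Section 2.3.3 says "Benefits include less oral and IV opiate use which also cause nausea, itching and respiratory depression", and section 3 justifies the primary endpoint with "Opiate use should be minimized due to side effects". For the study drug, 2.3.1 says "Risks can include nausea, vomiting, itching, respiratory depression", and 8.3.3.3 says "We expect to have cases of nausea and itching, we anticipate no cases of respiratory depression". Section 6.5.1 says "we provide the same rescue doses of medications for morphine including ondanstetron, diphenhydramine, and nalxone all as needed".

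**The concern.** Opiate consumption stands in here for something patients feel: the side effects of opiates. That works only if the intervention acts on side effects through the amount of oral and IV opiate taken. It does not, because the intervention is an opiate with its own nausea, vomiting, itching and respiratory depression. Less oral and IV opiate may reduce these effects and the epidural dose may add to them, so the net effect could go either way.

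Run as written, the trial could report lower consumption as a benefit with no comparison of side effects between the arms. If symptoms are also recorded only when someone mentions them, a table made afterwards would rest on incomplete counts, and a real harm or a real benefit could be missed.

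**Working it through.** **1. Reading the text.** The plan gives no safety figure to reproduce, so the main claim rests on setting the sections side by side.

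| Needed to check the side-effect rationale | What the plan provides |
|---|---|
| A symptom question put to every woman | Not named in 1.2, 1.3, 8.1 or 8.2; 8.3.5 does not say that every woman is asked |
| A by-arm summary of symptoms | None: 9.4.4 is N/A, and 9.1 and 9.4.1 to 9.4.3 name no adverse event |
| A by-arm summary of side-effect treatment | None, although 6.5.1 names the treatments and 8.3.3.1 grades severity by them |
| A by-arm summary of respiratory depression | None, although cases are monitored and reviewed |

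**2. What incomplete capture does (illustration).** The documents give neither side-effect rates nor a capture fraction, so both are assumed. The sample sizes come from 9.2: 150 per arm recruited, 60 per arm stated as needed.

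Let a fraction c of true events be captured in each arm. The observed rates are c·p1 and c·p2.

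- Risk ratio: (c·p2)/(c·p1) = p2/p1, unchanged.
- Risk difference: c·(p2 − p1), reduced by the factor c.
- 95% half-width: 1.96·√[q1(1−q1)/n + q2(1−q2)/n], with q = c·p.
- Power (two-sided 0.05, arcsine approximation, neglecting the opposite tail): Φ(h·√(n/2) − 1.96), with h = |2·arcsin√q2 − 2·arcsin√q1|.

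Worked example, 10% vs 20%, n = 150, c = 1: half-width 1.96·√[(0.09 + 0.16)/150] = 0.080. With h = 0.9273 − 0.6435 = 0.2838, power = Φ(0.2838·8.660 − 1.96) = Φ(0.498) = 0.69.

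With c = 0.5 (5% vs 10%): half-width 1.96·√[(0.0475 + 0.09)/150] = 0.059. With h = 0.6435 − 0.4510 = 0.1925, power = Φ(−0.293) = 0.385.

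| True rates | n per arm | Capture c | Difference | 95% half-width | Power |
|---|---|---|---|---|---|
| 10% vs 20% | 150 | 1 | 10 points | 8.0 | 69% |
| 10% vs 20% | 150 | 0.5 | 5 points | 5.9 | 39% |
| 10% vs 20% | 150 | 0.3 | 3 points | 4.7 | 25% |
| 10% vs 20% | 60 | 1 | 10 points | 12.7 | 34% |
| 10% vs 20% | 60 | 0.5 | 5 points | 9.4 | 18% |

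For 10% vs 30%, half capture lowers power from 99% to 85% at 150 per arm, and from 81% to 47% at 60. The pooled-variance formula gives nearly the same values (0.681 and 0.375 for the first two rows). Swapping the arms changes nothing, so a harm and a benefit are equally easy to miss.

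The intervals tell the same story without a test. At 150 per arm, the expected interval excludes zero with full capture (10 > 8.0) but not with half capture (5 < 5.9).

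**3. Respiratory depression.** If no case occurs among n women, the exact two-sided 95% upper limit is 1 − 0.025^(1/n). That is 2.4% for n = 150 and 6.0% for n = 60. Seeing no case is therefore still worth reporting by arm with its interval.

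**The case against.** The strongest reply is that adverse events are not ignored. Section 7.1 halts the study for review if respiratory depression occurs, 8.3.3.2 has each case assessed for relationship to treatment, and 10.1.6 has the principal investigator examine every adverse event. That is true, but these are reviews of single cases. Where nausea and itching are expected, case review cannot tell whether one arm has more of them.

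Second, no hypothesis claims fewer side effects; they appear only as rationale. This stands as a limit: the primary comparison is unaffected, and what goes untested is the reason given for caring about it.

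Third, capture may be better than assumed. Reports are received at follow-up, and neither the datasheets mentioned in 6.4 nor the items of the recovery score are shown. This also stands. The missing by-arm summary is certain, whereas the missing question is a matter of what is not stated. Even if the recovery score includes nausea, only the score itself is named for analysis.

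Fourth, the figures rest on assumed rates, and 60 per arm fits poorly with 7.3, which foresees almost no loss at 24 hours. The 150-per-arm rows are the more relevant ones, and the claim depends on none of them. Equal capture is also an assumption. Blinding supports it, but if severity differs by arm, capture may differ too. With a true 20% in both arms and capture of 0.5 and 0.3, the observed rates would be 10% and 6%, a spurious 4-point difference. That strengthens the case for asking everyone.

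**Conclusion.** The concern holds. The plan contains no by-arm summary of adverse events and names no symptom question at any scheduled contact, while side effects are the stated reason for the primary endpoint and the study drug carries the same risks. A finding of lower opiate consumption would therefore say nothing about the net side-effect burden.

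The size cannot be fixed from the documents. Under the assumed 10% vs 20% with 150 per arm, capturing half the events in each arm halves the risk difference and lowers power from 69% to 39%, with the risk ratio unchanged. The text-based conclusion needs none of these assumptions. This should be changed, but it does not threaten the validity of the primary test.

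**What to change.** **In 8.1, add:** *At the 24-hour contact every woman is asked, from a fixed checklist, whether she has had nausea, vomiting or itching since study drug administration (yes/no for each); if none was given, the period runs from its planned time. Receipt of each side-effect treatment named in 6.5.1 over the same period is recorded.*

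**In 9.4.4, replace N/A with:** *Nausea, vomiting, itching, respiratory depression (all cases reported under 8.3.6, with those meeting the definition in 8.3.2 also shown separately) and receipt of each treatment named in 6.5.1 will be summarized by randomized arm as counts and percentages, with the number of women asked, and as risk differences with 95% confidence intervals. These summaries are descriptive, without significance tests, and will be reported together with the primary result.*

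**Conforming edits:** add the checklist to 1.2 and 1.3, and add vomiting to 8.3.1, which lists only nausea and itching although 2.3.1 names vomiting as a risk.

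**Cost:** a few minutes per woman at a contact already planned, one SAP paragraph and one table. With no tests added, no multiplicity issue arises. The checklist needs to be in place while women are being enrolled, because symptoms not asked about cannot be reliably recovered later. Two limits remain: a checklist also picks up mild symptoms, and with 60 to 150 women per arm the intervals will not settle small differences.
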